7.2.1 Risks Associated with Pembrolizumab

Potential risks and toxicities associated with Pembrolizumab are detailed in the Investigator's Brochure.

7.2.2 Dose Modifications for Pembrolizumab

Pembrolizumab may be held up to 12 weeks for immune-related toxicity. If a patient has an immune-related toxicity that does not resolve within 12 weeks, pembrolizumab will be discontinued

AEs associated with pembrolizumab exposure may represent an immunologic etiology. These immune-related AEs (irAEs) may occur shortly after the first dose or several months after the last dose of pembrolizumab treatment and may affect more than one body system simultaneously. Therefore, early recognition and initiation of treatment is critical to reduce complications. Based on existing clinical study data, most irAEs were reversible and could be managed with interruptions of pembrolizumab, administration of corticosteroids and/or other supportive care.

PROTOCOL NUMBER: OSU-19132

For suspected irAEs, ensure adequate evaluation to confirm etiology or exclude other causes. Additional procedures or tests such as bronchoscopy, endoscopy, skin biopsy may be included as part of the evaluation. Based on the severity of irAEs, withhold or permanently discontinue pembrolizumab and administer corticosteroids. Dose modification and toxicity management guidelines for irAEs associated with pembrolizumab are provided below in Table 5.

7.3 Study Drug Discontinuation

If either ramucirumab or pembrolizumab is held or discontinued for toxicity, the remaining drug may be continued as maintenance therapy for up to 35 cycles or disease progression or unacceptable toxicity.

PROTOCOL NUMBER: OSU-19132

Table 5. Dose modifications and toxicity management guidelines for immune-related AEs associated with pembrolizumab

General instructions:				
Immune-related AEs	Toxicity grade or conditions (CTCAEv5.0)	Action taken to pembrolizumab	irAE management with corticosteroid and/or other therapies	Monitor and follow-up
Pneumonitis	Grade 2	Withhold	
 Administer corticosteroids (initial dose of 1-2 mg/kg prednisone or equivalent) followed by taper 	
 Monitor participants for signs and symptoms of pneumonitis Evaluate participants with suspected pneumonitis with radiographic imaging and initiate corticosteroid treatment Add prophylactic antibiotics for opportunistic infections
	Grade 3 or 4, or recurrent Grade 2	Permanently discontinue		
Diarrhea / Colitis	Grade 2 or 3	Withhold	
 Administer corticosteroids (initial dose of 1-2 mg/kg prednisone or equivalent) followed by taper 	
 Monitor participants for signs and symptoms of enterocolitis (ie, diarrhea, abdominal pain, blood or mucus in stool with or without fever) and of bowel perforation (ie, peritoneal signs and ileus). Participants with \geq Grade 2 diarrhea suspecting colitis should consider GI consultation and performing endoscopy to rule out colitis. Participants with diarrhea/colitis should be advised to drink liberal quantities of clear fluids. If sufficient oral fluid intake is not feasible, fluid and electrolytes should be substituted via IV infusion.
	Recurrent Grade 3 or Grade 4	Permanently discontinue		

CONFIDENTIAL

PROTOCOL NUMBER: OSU-19132

AST / ALT elevation or Increased bilirubin	Grade 2	Withhold	
 Administer corticosteroids (initial dose of 0.5- 1 mg/kg prednisone or equivalent) followed by taper 	
 Monitor with liver function tests (consider weekly or more frequently until liver enzyme value returned to baseline or is stable)
	Grade 3 or 4	Permanently discontinue	
 Administer corticosteroids (initial dose of 1-2 mg/kg prednisone or equivalent) followed by taper 	
Type 1 diabetes mellitus (T1DM) or Hyperglycemia	Newly onset T1DM or Grade 3 or 4 hyperglycemia associated with evidence of β -cell failure	Withhold	
 Initiate insulin replacement therapy for participants with T1DM Administer anti-hyperglycemic in participants with hyperglycemia 	
 Monitor participants for hyperglycemia or other signs and symptoms of diabetes.
Hypophysitis	Grade 2	Withhold	
 Administer corticosteroids and initiate hormonal replacements as clinically indicated. 	
 Monitor for signs and symptoms of hypophysitis (including hypopituitarism and adrenal insufficiency)
	Grade 3 or 4	Withhold or permanently discontinue ¹		
Hyperthyroidism	Grade 2	Continue	
 Treat with non-selective beta-blockers (eg, propranolol) or thionamides as appropriate 	
 Monitor for signs and symptoms of thyroid disorders.
	Grade 3 or 4	Withhold or permanently discontinue ¹		

PROTOCOL NUMBER: OSU-19132

Hypothyroidism	Grade 2-4	Continue	
 Initiate thyroid replacement hormones (eg, levothyroxine or liothyroinine) per standard of care 	
 Monitor for signs and symptoms of thyroid disorders.
Nephritis and Renal dysfunction	Grade 2	Withhold	
 Administer corticosteroids (prednisone 1-2 mg/kg or equivalent) followed by taper. 	
 Monitor changes of renal function
	Grade 3 or 4	Permanently discontinue		
Myocarditis	Grade 1 or 2	Withhold	
 Based on severity of AE administer corticosteroids 	
 Ensure adequate evaluation to confirm etiology and/or exclude other causes
	Grade 3 or 4	Permanently discontinue		
All other immune-related AEs	Intolerable/persistent Grade 2	Withhold	
 Based on type and severity of AE administer corticosteroids 	
 Ensure adequate evaluation to confirm etiology and/or exclude other causes
	Grade 3	Withhold or discontinue based on the type of event. Events that require discontinuation include and not limited to: Gullain-Barre Syndrome, encephalitis		
	Grade 4 or recurrent Grade 3	Permanently discontinue		

PROTOCOL NUMBER: OSU-19132

1. Withhold or permanently discontinue pembrolizumab is at the discretion of the investigator or treating physician.

NOTE:

For participants with Grade 3 or 4 immune-related endocrinopathy where withhold of pembrolizumab is required, pembrolizumab may be resumed when AE resolves to \leq Grade 2 and is controlled with hormonal replacement therapy or achieved metabolic control (in case of T1DM).

Table 6. Pembrolizumab Infusion Reaction Dose modification and Treatment Guidelines

PROTOCOL NUMBER: OSU-19132

NCI CTCAE Grade	Treatment	Premedication at Subsequent Dosing
Grade 1 Mild reaction; infusion interruption not indicated; intervention not indicated	Increase monitoring of vital signs as medically indicated until the participant is deemed medically stable in the opinion of the investigator.	None
Grade 2 Requires therapy or infusion interruption but responds promptly to symptomatic treatment (e.g., antihistamines, NSAIDs, narcotics, IV fluids); prophylactic medications indicated for ≤ 24 hrs	
Stop Infusion. Additional appropriate medical therapy may include but is not limited to: IV fluids Antihistamines NSAIDs Acetaminophen Narcotics
 
Increase monitoring of vital signs as medically indicated until the participant is deemed medically stable in the opinion of the investigator.
 
If symptoms resolve within 1 hour of stopping drug infusion, the infusion may be restarted at 50% of the original infusion rate (e.g. from 100 mL/hr to 50 mL/hr). Otherwise dosing will be held until symptoms resolve and the participant should be premedicated for the next scheduled dose.
 
Participants who develop Grade 2 toxicity despite adequate premedication should be permanently discontinued from further study drug treatment
	Participant may be premedicated 1.5h (± 30 minutes) prior to infusion of _____ with: Diphenhydramine 50 mg po (or equivalent dose of antihistamine). Acetaminophen 500- 1000 mg po (or equivalent dose of analgesic).
Grades 3 or 4 Grade 3: Prolonged (i.e., not rapidly responsive to symptomatic medication and/or brief interruption of infusion); recurrence of symptoms following initial improvement;	
Stop Infusion. Additional appropriate medical therapy may include but is not limited to: Epinephrine** IV fluids Antihistamines NSAIDs Acetaminophen Narcotics Oxygen Pressors
	No subsequent dosing

PROTOCOL NUMBER: OSU-19132

hospitalization indicated for other clinical sequelae (e.g., renal impairment, pulmonary infiltrates) Grade 4: Life-threatening; pressor or ventilatory support indicated	Corticosteroids Increase monitoring of vital signs as medically indicated until the participant is deemed medically stable in the opinion of the investigator. Hospitalization may be indicated. **In cases of anaphylaxis, epinephrine should be used immediately. Participant is permanently discontinued from further study drug treatment.	

Appropriate resuscitation equipment should be available at the bedside and a physician readily available during the period of drug administration.
 
For further information, please refer to the Common Terminology Criteria for Adverse Events v5.0 (CTCAE) at http://ctep.cancer.gov
		

7.3.1 Dose modification and toxicity management of infusion-reactions related to pembrolizumab

Pembrolizumab may cause severe or life threatening infusion-reactions including severe hypersensitivity or anaphylaxis. Signs and symptoms usually develop during or shortly after drug infusion and generally resolve completely within 24 hours of completion of infusion. Dose modification and toxicity management guidelines on pembrolizumab associated infusion reaction are provided in Table 6.

7.3.2 Other allowed dose interruption for pembrolizumab

Pembrolizumab may be interrupted for situations other than treatment-related AEs such as medical / surgical events or logistical reasons not related to study therapy. Participants should be placed back on study therapy within 3 weeks of the scheduled interruption, unless otherwise discussed with the Sponsor. The reason for interruption should be documented in the patient's study record.

8. SUPPORTIVE CARE GUIDELINES

8.1 Concomitant Medications

Medications or vaccinations specifically prohibited in the exclusion criteria are not allowed during the ongoing trial. If there is a clinical indication for one of these or other medications or vaccinations specifically prohibited during the trial, discontinuation from trial therapy or vaccination may be required. The final decision on any supportive therapy or vaccination rests with the investigator and/or the participants's primary physician.

8.2 Permitted Concomitant Medication

Patients will receive concomitant medications to treat symptoms, AEs and intercurrent illnesses that are medically necessary as standard care. Medications to treat concomitant diseases like diabetes, hypertension, etc., are allowed.

8.3 Glucocorticoid therapy

Glucocorticoids (≤ 20 mg oral prednisone or equivalent) per day are permitted at baseline and during the study for non-malignant conditions (i.e., asthma, irritable bowel disease, etc.,) as needed, but patients should preferably have been on a stable dose for at least two weeks before study entry.

8.4 Prohibited Medication

Participants are prohibited from receiving the following therapies during the Screening and Treatment Phase (including retreatment for post-complete response relapse) of this trial:

- Antineoplastic systemic chemotherapy or biological therapy
- Immunotherapy not specified in this protocol
- Chemotherapy not specified in this protocol
- Investigational agents other than pembrolizumab
- Chronic antiplatelet therapy, including aspirin, nonsteroidal anti-inflammatory drugs (NSAIDs, including ibuprofen, naproxen, and others), dipyridamole or clopidogrel, or similar agents is not permitted. Once-daily aspirin use (maximum dose 325 mg/day) is permitted.
- Radiation therapy
 - Note: Radiation therapy to the brain may be allowed after consultation with the PI for patients receiving clinical benefit. See section 6.3.5. . Ramucirumab therapy should be temporarily discontinued for 2 weeks prior to starting radiation. However,

starting radiation sooner is permissible if the investigator considers that the benefits outweigh the risks for the patient. Patient can have radiation for CNS oligoprogression as long as ramucirumab is held for 4-6 weeks afterwards. Ramucirumab can be restarted after this time if the patient is asymptomatic, clinically stable and this is considered appropriate by the investigator.

- Live vaccines within 30 days prior to the first dose of study treatment and while participating in the study. Examples of live vaccines include, but are not limited to, the following: measles, mumps, rubella, varicella/zoster, yellow fever, rabies, BCG, and typhoid vaccine. Seasonal influenza vaccines for injection are generally killed virus vaccines and are allowed; however, intranasal influenza vaccines (eg, FluMist®) are live attenuated vaccines and are not allowed.
- Systemic glucocorticoids for any purpose other than to modulate symptoms from an event of clinical interest of suspected immunologic etiology. The use of physiologic doses of corticosteroids may be approved after consultation with the Sponsor.

Participants who, in the assessment by the investigator, require the use of any of the aforementioned treatments for clinical management should be removed from the study. All treatments that the Investigator considers necessary for a participant's welfare may be administered at the discretion of the Investigator in keeping with the community standards of medical care.

Medications or vaccinations specifically prohibited in the exclusion criteria are not allowed during the ongoing study. If there is a clinical indication for any medication or vaccination specifically prohibited during the study, discontinuation from study therapy or vaccination may be required. The final decision on any supportive therapy or vaccination rests with the investigator and/or the participant's primary physician. However, the decision to continue the participant on study treatment requires the mutual agreement of the investigator, the Sponsor and the participant.

There are no prohibited therapies during the Post-Treatment Follow-up Phase.

8.5 Rescue Medications & Supportive Care

Participants should receive appropriate supportive care measures as deemed necessary by the treating investigator. Suggested supportive care measures for the management of AEs with potential immunologic etiology are outlined along with the dose modification guidelines in Section 7.2.2 [Table 5]. Where appropriate, these guidelines include the use of oral or IV treatment with corticosteroids, as well as additional anti-inflammatory agents if symptoms do not improve with administration of corticosteroids. Note that several courses of steroid tapering may be necessary as symptoms may worsen when the steroid dose is decreased. For each disorder, attempts should be made to rule out other causes such as metastatic disease or bacterial or viral infection, which might require additional supportive care. The treatment guidelines are intended to be applied when the Investigator determines the events to be related to pembrolizumab.

8.6 Dose Adjustments for Weight

Ramucirumab dose will be adjusted if patient has > 10% change in weight from weight used to calculate previous dose. No weight based dose adjustment is required for pembrolizumab.

9. STATISTICAL CONSIDERATIONS

9.1 Endpoints

9.1.1 Primary Endpoint

Overall response rate will be evaluated using both RECIST and iRECIST criteria. Patients will have repeat imaging every 6 weeks to assess response.

9.1.2 Secondary Endpoints

- Safety and tolerability as measured by adverse events
- Clinical benefit rate – CR+PR+SD
- Survival – progression-free and overall

9.1.3 Exploratory Endpoints (Correlative Studies)

To characterize predictive immunologic biomarkers of response in tissue and peripheral blood

- T cell receptor (TCR) immunosequencing in peripheral blood (before and after treatment) and tumor tissue (at baseline) with clinical response.
- CyTOF from peripheral blood and infiltrating immune cells in tissue at baseline and after treatment
- Circulating VEGF in peripheral blood at baseline and after treatment with clinical response

9.2 Sample Size Justification

Response rate with single agent IO is around 10% and we would consider a response rate of at least 25% to be interesting for further study. The optimal two-stage design to test the null hypothesis that $P \leq 0.10$ versus the alternative that $P \geq 0.25$ will include 13 patients in the first stage. After testing the drug on 13 patients in the first stage, the trial will be terminated if 1 or fewer respond. If the trial goes on to the second stage, an additional 21 patients will be included for a total of 34 patients studied.

9.3 Planned Interim Analysis

After testing the drug on 13 patients in the first stage, the trial will be terminated if no patients respond. If the trial goes on to the second stage, an additional 21 patients will be included for a total of 34 patients studied.

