	
Tumor type: EGFR mutation positive NSCLC
 
The proposed study will be an open-label single arm phase II trial of ramucirumab and pembrolizumab (R+P) in EGFR mutant NSCLC after progression on tyrosine kinase inhibitors (TKIs). Patients are required to receive at least one TKI (erlotinib, gefitinib, afatinib or osimertinib). Post-TKI chemotherapy is also permitted.
 
Each treatment cycle will be 21 days; patients will receive ramucirumab 10 mg/kg IV and pembrolizumab 200 mg IV and on day 1. Dosing of ramucirumab and pembrolizumab is based on prior phase 1 testing of the combination. A two-stage design will be utilized to minimize exposure to combination therapy if there is limited efficacy. The initial stage will enroll 13 patients; if ≥ 1 patient has a confirmed response, the study will continue and enroll an additional 21 patients for a total of 34 patients.
 
Response will be assessed using RECIST (RECIST 1.1 and iRECIST). Imaging will be performed every 6 weeks/2 cycles to assess response. Patients with clinical benefit may continue therapy beyond progression for up to 2 cycles – if progressive disease confirmed on repeat imaging, therapy would be discontinued. Toxicity will be assessed using CTCAE v5.0. Progression free survival will be assessed using RECIST and will be assessed starting from date of study enrollment.
 
Blood samples tissue will be collected at baseline (day 1, cycle 1), cycle 3 day1 (approx. 6 weeks), and at study discontinuation (or progression). Archival tissue will be requested at enrollment for correlative studies.

Duration of Treatment	Patients may continue to receive study treatment (R+P) until radiographic documentation of disease progression, the occurrence of unacceptable toxicity or of the occurrence of other withdrawal criteria. If either drug is discontinued due to toxicity, the other drug may be continued.
Inclusion /Exclusion Criteria	
Inclusion Criteria:
 
1. Adult patients aged ≥ 18 years

IRB Protocol Number: 2019C0145
IRB Approval date: 06/10/2022
Version: 05/06/2022

PROTOCOL NUMBER: OSU-19132

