Statistical Analysis	
The primary study objective is to assess the overall response rate (ORR) of ramucirumab and pembrolizumab. The study will use Simon's two-stage design. Response rate with single agent IO is around 10% and we would consider a response rate of at least 25% to be interesting for further study. The initial stage will include 13 patients; the trial will be terminated if there are no responses. If the trial goes on to the second stage, an additional 21 patients will be included for a total of 34 patients studied.
 
Secondary objectives involve evaluating safety and tolerability and estimating PFS and overall survival. Descriptive statistics will be calculated for these outcomes and Kaplan-Meier curves will be calculated to estimate PFS and OS. Patients who have reached the end of the study but not progressed will be considered censored at the last documented date of contact. Estimates from this analysis will be used as preliminary data to inform future research.

IRB Protocol Number: 2019C0145
IRB Approval date: 06/10/2022
Version: 05/06/2022

PROTOCOL NUMBER: OSU-19132

LIST OF ABBREVIATIONS AND DEFINITIONS OF TERMS

ADR	Adverse Drug Reaction
AE	Adverse event
ALT (SGPT)	Alanine aminotransferase
ANC	Absolute neutrophil count
APC	Adenomatous polyposis coli
API	Active pharmaceutical ingredient
AST (SGOT)	Aspartate aminotransferase
AUC	Area under the curve
BMI	Body mass index
BSA	Body surface area
BUN	Blood urea nitrogen
BW	Body weight
CBC	Complete blood count
CI	Confidence interval
CK	Creatine kinase
CNS	Central nervous system
CR	Complete response
CRF	Case report form
CRO	Contract research organisation
CTCAE	Common terminology criteria for adverse events
CT Scan	Computed Tomography Scan
CYP450	Cytochrome P450
DCR	Disease control rate
DLT	Dose-limiting toxicity
DNA	Desoxyribonucleic acid
ECG	Electrocardiogram
ECOG	Eastern Cooperative Oncology Group
EOT	End of treatment
FU	Follow-up
GCP	Good Clinical Practice
GI	Gastrointestinal
GLP	Good laboratory practice
h	Hour
HR	Hazard ratio
IA	Interim analysis
IMP	Investigational medicinal product
INR	International normalized ratio
IRB	Institutional review board
ITT	Intent to treat
i.v.	Intravenous
KRAS	Kirsten Rat sarcoma
LDH	Lactate dehydrogenase
m ²	Square metre (body surface area)

IRB Protocol Number: 2019C0145
IRB Approval date: 06/10/2022
Version: 05/06/2022

PROTOCOL NUMBER: OSU-19132

mg	Milligram
min	Minute
mL	Millilitre
MRI	Magnetic resonance imaging
MTD	Maximum tolerated dose

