9.4 Analysis Plan

9.4.1 Primary endpoint analysis:

The primary study objective is to assess the overall response rate (ORR) of ramucirumab plus pembrolizumab. To do so, we will use Simon's two-stage design.²⁰ This design is implemented by first enrolling a small group of patients and then enrolling a second group of patients in the second stage conditional on an adequate number of responses in the first group. Response rate with single agent IO is around 10% and we would consider a response rate of at least 25% to be interesting for further study. The optimal two-stage design to test the null hypothesis that $P \leq 0.10$ versus the alternative that $P \geq 0.25$ will include 13 patients in the first stage. After testing the drug on 13 patients in the first stage, the trial will be terminated if 1 or fewer respond. If the trial goes on to the second stage, an additional 21 patients will be included for a total of 34 patients studied. If the

total number responding is less than or equal to 5, the drug is rejected. This design has an expected sample size of 20.95 and a probability of early termination of 0.621. The sample size was calculated using PASS 16 and assuming $\alpha = 0.10$ with a desired power of 80%.

Overall survival and progression-free survival as continuous time-to-event outcomes: All evaluable patients will be used for this analysis. Kaplan-Meier curves will be used to estimate overall survival, measured from the date of study registration to the date of event (i.e., death) or the date of last follow-up if no event has occurred at their last evaluation. We will further consider Cox proportional hazards models to explore a limited set of confounding factors.

9.4.2 Analysis of secondary endpoints:

Secondary objectives involve evaluating safety and tolerability and estimating PFS and overall survival. Descriptive statistics will be calculated for these outcomes and Kaplan-Meier curves will be calculated to estimate PFS and OS. Patients who have reached the end of the study but not progressed will be considered censored at the last documented date of contact. Estimates from this analysis will be used as preliminary data to inform future research.

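### The stage-1 futility rule is written two ways (stop at 0 of 13, or at 1 or fewer of 13), and the stated alpha, early-termination probability and expected sample size hold only under the second

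*Combined protocol and SAP*

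**What the plan says.** The combined protocol and SAP states the stage-1 rule five times, in two incompatible forms.

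- **Stop at 1 or fewer of 13.** Section 9.2 reads "After testing the drug on 13 patients in the first stage, the trial will be terminated if 1 or fewer respond". Section 9.4.1 repeats this rule, adds the final boundary (the drug is rejected if 5 or fewer of 34 respond) and gives the design's properties: "This design has an expected sample size of 20.95 and a probability of early termination of 0.621". It also states an alpha of 0.10 and a desired power of 80%.
- **Stop only at 0 of 13.** Section 9.3, Planned Interim Analysis, reads "After testing the drug on 13 patients in the first stage, the trial will be terminated if no patients respond". The Statistical Analysis row of the synopsis says "The initial stage will include 13 patients; the trial will be terminated if there are no responses". The Study Design row of the synopsis gives the same rule from the other side: if at least one "patient has a confirmed response, the study will continue and enroll an additional 21 patients".

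All five statements are current text in one version of the protocol.

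**The concern.** The two forms agree at 0 responders and at 2 or more. They give opposite instructions at exactly 1, which is a likely count if the regimen is no better than single-agent immunotherapy. This is the trial's only interim efficacy rule, and the synopsis justifies the two-stage design by the wish to limit exposure to an ineffective combination. A wrong continuation commits 21 more patients, which is 21 × 2 = 42 months at the accrual rate of one patient every two months in section 3.2. Section 3.1.4 also makes possible expansion to further sites depend on this analysis.

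The properties in section 9.4.1 belong to a specific rule. If the trial runs on the other rule, the reported type I error and the chance of early stopping are no longer those of the trial conducted. If the conflict is settled only once the stage-1 count is known, the choice of rule depends on the data.

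**Working it through.** **Inputs.** Null and target response rates p0 = 0.10 and p1 = 0.25, stage sizes n1 = 13 and n2 = 21 (N = 34), and final cutoff r = 5 (success needs 6 or more of 34), all from section 9.4.1. The stage-1 cutoff r1 is 1 (sections 9.2 and 9.4.1) or 0 (section 9.3 and synopsis).

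**Formulas (exact binomial).** X1 ~ Bin(13, p) and X2 ~ Bin(21, p), independent.

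- Probability of early termination: PET = P(X1 ≤ r1).
- Expected sample size: EN = 13 + (1 − PET) × 21.
- Probability of declaring the drug active: sum over x > r1 of P(X1 = x) × P(X2 ≥ r + 1 − x). At p = 0.10 this is alpha; at p = 0.25 it is power.

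**Step 1: reproduce the plan's figures with r1 = 1.** At p = 0.10:

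- P(X1 = 0) = 0.9^13 = 0.2542
- P(X1 = 1) = 13 × 0.1 × 0.9^12 = 0.3672
- PET = 0.2542 + 0.3672 = 0.6213 (unrounded terms; stated 0.621)
- EN = 13 + 0.3787 × 21 = 20.95 (stated 20.95)
- alpha = 0.0957 (target 0.10) and power = 0.8108 (target 0.80)

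A search over two-stage designs for these rates, with alpha at most 0.10 and power at least 0.80, also returns 1/13 and 5/34 as the optimal design. Section 9.4.1 is therefore correct for the 1-or-fewer rule.

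**Step 2: change only the stage-1 cutoff to r1 = 0.**

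- PET = 0.2542
- EN = 13 + 0.7458 × 21 = 28.66
- Trials with exactly 1 responder now continue and need at least 5 of the next 21. At p = 0.10, P(X2 ≥ 5) = 0.0522, so alpha rises by 0.3672 × 0.0522 = 0.0191, to 0.1149.
- At p = 0.25, P(X1 = 1) = 0.1029 and P(X2 ≥ 5) = 0.6326, so power rises by 0.1029 × 0.6326 = 0.0651, to 0.8759.

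**Step 3: try other final cutoffs with r1 = 0.**

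| r1 | r | alpha | power | PET at 0.10 | EN at 0.10 |
|---|---|---|---|---|---|
| 1 | 5 | 0.0957 | 0.811 | 0.621 | 20.95 |
| 0 | 4 | 0.236 | 0.936 | 0.254 | 28.66 |
| 0 | 5 | 0.115 | 0.876 | 0.254 | 28.66 |
| 0 | 6 | 0.047 | 0.776 | 0.254 | 28.66 |

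Alpha and power both fall as r rises. Every cutoff of 5 or lower breaks the alpha target and every cutoff of 6 or higher breaks the power target, so none at N = 34 meets both.

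**Step 4: how often the two rules conflict.** P(exactly 1 of 13) is 36.7% at a response rate of 10% and 10.3% at 25%.

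**The case against.** Only the 1-or-fewer rule reproduces 20.95 and 0.621, and section 9.4.1 is the one complete statement of the design. A careful reader can infer which rule was meant, and could call the other three statements drafting slips. The inference is reasonable and makes the correction easy. It does not settle the matter, because three of the five statements say otherwise, one of them in the section devoted to the interim analysis, and no order of precedence is given.

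The statistical damage should also not be overstated, and these limits stand:

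- The alpha excess is modest (0.115 against 0.10) and assumes the final cutoff of 5 of 34 is kept. It is the only cutoff the plan gives.
- Power is not lost under the zero-response rule; 0.876 also meets the 80% target.
- The large effects are on early stopping and expected sample size. The chance of finally declaring an inactive regimen active moves only from 0.096 to 0.115.
- This is not the trial's only decision rule. Section 9.4.1 has the final cutoff, and sections 6.2 and 6.7 allow termination on safety or conduct grounds.

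A related gap is separate from the cutoff. The Study Design row of the synopsis counts a confirmed response, while sections 9.2, 9.3 and 9.4.1 do not mention confirmation. Section 6.3.5 places the confirming scan at least 4 weeks after the first response, and section 4.1 allows the interim after 6 weeks of follow-up.

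**Conclusion.** The concern holds. The stage-1 decision is undefined at exactly 1 of 13 responders, an outcome with probability 36.7% under the null rate and 10.3% under the target rate. The arithmetic in section 9.4.1 is right, but only for the 1-or-fewer rule. Under the rule in section 9.3 and the synopsis, with the final cutoff unchanged, the chance of stopping early for an inactive regimen falls by more than half (0.621 to 0.254), about 7.7 more patients are expected to be enrolled (28.66 − 20.95), and alpha exceeds its stated level (0.115 against 0.10). The results assume independent responses with a common rate and exactly 13 and 34 patients in the analysis. The plan needs correcting because the fault lies in the interim decision rule for the primary endpoint.

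**What to change.** State one rule in all five places, preferably before the stage-1 responses are known.

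- **Option 1.** Change section 9.3 and the Study Design and Statistical Analysis rows of the synopsis to terminate at 1 or fewer of 13. This matches sections 9.2 and 9.4.1, and no figure changes.
- **Option 2.** If the trial has already continued, or will continue, on a single response, change sections 9.2 and 9.4.1 to the zero-response rule. Restate the properties with cutoff 5 of 34: alpha 0.115, power 0.876, early termination 0.254, expected sample size 28.7. Drop the claims of an optimal design and of alpha 0.10. If the stage-1 count was known when the rule was settled, report that as a deviation.

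In either case, say in the same sentence whether a stage-1 responder needs a confirmed response, and make the interim timing consistent with that.

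The cost is a wording amendment. The maximum stays at 34 patients under both options. Option 2 carries the higher expected enrolment under the null (28.7 against 20.95).
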